## 13 STUDY MONITORING

### 13.1 RESPONSIBILITIES OF THE INVESTIGATOR(S)

The investigator is required to ensure compliance with all procedures required by the clinical trial protocol and with all study procedures provided by the sponsor (including security rules). The investigator agrees to provide reliable data and all information requested by the clinical trial protocol (with the help of the e-CRF, Discrepancy Resolution Form [DRF] or other appropriate instrument) in an accurate and legible manner according to the instructions provided and to ensure direct access to source documents by sponsor representatives.

If any circuit includes transfer of data particular attention should be paid to the confidentiality of the patient's data to be transferred.

The investigator may appoint such other individuals as he/she may deem appropriate as subinvestigators to assist in the conduct of the clinical trial in accordance with the clinical trial protocol. All subinvestigators shall be appointed and listed in a timely manner. The subinvestigators will be supervised by and work under the responsibility of the investigator. The investigator will provide them with a copy of the clinical trial protocol and all necessary information.

### 13.2 RESPONSIBILITIES OF THE SPONSOR

The sponsor of this clinical trial is responsible to regulatory authorities for taking all reasonable steps to ensure the proper conduct of the clinical trial as regards ethics, clinical trial protocol compliance, and integrity and validity of the data recorded on the e-CRFs. Thus, the main duty of the monitoring team is to help the investigator and the sponsor maintain a high level of ethical, scientific, technical and regulatory quality in all aspects of the clinical trial.

At regular intervals during the clinical trial, the site will be contacted, through monitoring visits, letters or telephone calls, by a representative of the monitoring team to review study progress, investigator and patient compliance with clinical trial protocol requirements and any emergent problems. These monitoring visits will include but not be limited to review of the following aspects: patient informed consent, patient recruitment and follow-up, SAE documentation and reporting, AESI documentation and reporting, AE documentation, IMP allocation, patient compliance with the IMP regimen, IMP accountability, concomitant therapy use and quality of data.

### **13.3 SOURCE DOCUMENT REQUIREMENTS**

According to the ICH GCP, the monitoring team must check the e-CRF entries against the source documents, except for the pre-identified source data directly recorded in the e-CRF. The informed consent form will include a statement by which the patient allows the sponsor's duly authorized personnel, the Ethics Committee (IRB/IEC), and the regulatory authorities to have direct access to original medical records which support the data on the e-CRFs (eg, patient's medical file, appointment books, original laboratory records, etc). These personnel, bound by professional secrecy, must maintain the confidentiality of all personal identity or personal medical information (according to confidentiality and personal data protection rules).

### **13.4 USE AND COMPLETION OF CASE REPORT FORMS (CRFS) AND ADDITIONAL REQUEST**

It is the responsibility of the investigator to maintain adequate and accurate e-CRFs (according to the technology used) designed by the sponsor to record (according to sponsor instructions) all observations and other data pertinent to the clinical investigation in a timely manner. All CRFs should be completed in their entirety in a neat, legible manner to ensure accurate interpretation of data.

Should a correction be made, the corrected information will be entered in the e-CRF overwriting the initial information. An audit trail allows identifying the modification.

Data are available within the system to the sponsor as soon as they are entered in the e-CRF.

The computerized handling of the data by the sponsor may generate additional requests (DRF) to which the investigator is obliged to respond by confirming or modifying the data questioned. The requests with their responses will be managed through the e-CRF.

### **13.5 USE OF COMPUTERIZED SYSTEMS**

The complete list of computerized systems used for the study is provided in a separate document which is maintained in the sponsor and investigator study files.

## **14 ADDITIONAL REQUIREMENTS**

### **14.1 CURRICULUM VITAE**

A current copy of the curriculum vitae describing the experience, qualification and training of each investigator and subinvestigator will be signed, dated and provided to the sponsor prior to the beginning of the clinical trial.

### **14.2 RECORD RETENTION IN STUDY SITES**

The investigator must maintain confidential all study documentation, and take measures to prevent accidental or premature destruction of these documents.

The investigator should retain the study documents at least 15 years after the completion or discontinuation of the clinical trial.

However, applicable regulatory requirements should be taken into account in the event that a longer period is required.

The investigator must notify the sponsor prior to destroying any study essential documents following the clinical trial completion or discontinuation.

If the investigator's personal situation is such that archiving can no longer be ensured by him/her, the investigator shall inform the sponsor and the relevant records shall be transferred to a mutually agreed upon designee.

### **14.3 CONFIDENTIALITY**

All information disclosed or provided by the sponsor (or any company/institution acting on their behalf), or produced during the clinical trial, including, but not limited to, the clinical trial protocol, personal data in relation to the patients, the e-CRFs, the investigator's Brochure and the results obtained during the course of the clinical trial, is confidential, prior to the publication of results. The investigator and any person under his/her authority agree to undertake to keep confidential and not to disclose the information to any third party without the prior written approval of the sponsor.

However, the submission of this clinical trial protocol and other necessary documentation to the Ethics committee (IRB/IEC) is expressly permitted, the IRB/IEC members having the same obligation of confidentiality.

The subinvestigators shall be bound by the same obligation as the investigator. The investigator shall inform the subinvestigators of the confidential nature of the clinical trial.

The investigator and the subinvestigators shall use the information solely for the purposes of the clinical trial, to the exclusion of any use for their own or for a third party's account.

#### **14.4 PROPERTY RIGHTS**

All information, documents and IMP provided by the sponsor or its designee are and remain the sole property of the sponsor.

The investigator shall not and shall cause the delegated investigator staff/subinvestigator not to mention any information or the Product in any application for a patent or for any other intellectual property rights.

All the results, data, documents and inventions, which arise directly or indirectly from the clinical trial in any form, shall be the immediate and exclusive property of the sponsor.

The sponsor may use or exploit all the results at its own discretion, without any limitation to its property right (territory, field, continuance). The sponsor shall be under no obligation to patent, develop, market or otherwise use the results of the clinical trial.

As the case may be, the investigator and/or the subinvestigators shall provide all assistance required by the sponsor, at the sponsor's expense, for obtaining and defending any patent, including signature of legal documents.

#### **14.5 DATA PROTECTION**

- The patient's personal data, which are included in the sponsor database shall be treated in compliance with all applicable laws and regulations.
- When archiving or processing personal data pertaining to the investigator and/or to the patients, the sponsor shall take all appropriate measures to safeguard and prevent access to this data by any unauthorized third party.
- The sponsor also collects specific data regarding investigator as well as personal data from any person involved in the study which may be included in the sponsor's databases, shall be treated by both the sponsor and the investigator in compliance with all applicable laws and regulations.
- Subject race or ethnicity (ethnicity: not Hispanic or Latino; race: American Indian or Alaska native, Asian, Black, Native Hawaiian or other Pacific Islander, White and "not reported") will be collected in this study because these data are required by several health authorities.

#### **14.6 INSURANCE COMPENSATION**

The sponsor certifies that it has taken out a liability insurance policy covering all clinical trials under its sponsorship. This insurance policy is in accordance with local laws and requirements. The insurance of the sponsor does not relieve the investigator and the collaborators from any obligation to maintain their own liability insurance policy. An insurance certificate will be provided to the IECs/IRBs or regulatory authorities in countries requiring this document.

## **14.7 SPONSOR AUDITS AND INSPECTIONS BY REGULATORY AGENCIES**

For the purpose of ensuring compliance with the clinical trial protocol, Good Clinical Practice and applicable regulatory requirements, the investigator should permit auditing by or on the behalf of the sponsor and inspection by regulatory authorities.

The investigator agrees to allow the auditorsinspectors to have direct access to his/her study records for review, being understood that these personnel is bound by professional secrecy, and as such will not disclose any personal identity or personal medical information.

The investigator will make every effort to help with the performance of the audits and inspections, giving access to all necessary facilities, data, and documents.

As soon as the investigator is notified of a planned inspection by the authorities, he will inform the sponsor and authorize the sponsor to participate in this inspection.

The confidentiality of the data verified and the protection of the patients should be respected during these inspections.

Any result and information arising from the inspections by the regulatory authorities will be immediately communicated by the investigator to the sponsor.

The investigator shall take appropriate measures required by the sponsor to take corrective actions for all problems found during the audit or inspections.

## **14.8 PREMATURE DISCONTINUATION OF THE STUDY OR PREMATURE CLOSE-OUT OF A SITE**

### **14.8.1 By the sponsor**

The sponsor has the right to terminate the participation of either an individual site or the study at any time, for any reason, including but not limited to the following:

- The information on the product leads to doubt as to the benefit/risk ratio;
- Patient enrollment is unsatisfactory;
- The investigator has received from the sponsor all IMP, means and information necessary to perform the clinical trial and has not included any patient after a reasonable period of time mutually agreed upon;
- Non-compliance of the investigator or sub-investigator, delegated staff with any provision of the clinical trial protocol, and breach of the applicable laws and regulations or breach of the ICH GCP;
- The total number of patients are included earlier than expected;

In any case the sponsor will notify the investigator of its decision by written notice.

#### **14.8.2 By the Investigator**

The investigator may terminate his/her participation upon thirty (30) days' prior written notice if the study site or the investigator for any reason becomes unable to perform or complete the clinical trial.

In the event of premature discontinuation of the study or premature close-out of a site, for any reason whatsoever, the appropriate IRB/IEC and regulatory authorities should be informed according to applicable regulatory requirements.

#### **14.9 CLINICAL TRIAL RESULTS**

The sponsor will be responsible for preparing a clinical study report and to provide a summary of study results to the investigator. The coordinating investigator who will sign off on the study report will be the investigator who first enrolled the largest number of patients in the trial.

#### **14.10 PUBLICATIONS AND COMMUNICATIONS**

The investigator undertakes not to make any publication or release pertaining to the study and/or results of the study prior to the sponsor's written consent, being understood that the sponsor will not unreasonably withhold its approval.

As the study is being conducted at multiple sites, the sponsor agrees that, consistent with scientific standards, a primary presentation or publication of the study results based on global study outcomes shall be sought. However, if no multicenter publication is submitted, underway or planned within twelve (12) months of the completion of this study at all sites, the investigator shall have the right to publish or present independently the results of this study in agreement with other investigators and stakeholders. The investigator shall provide the sponsor with a copy of any such presentation or publication for review and comment at least 30 days in advance of any presentation or submission for publication. In addition, if requested by the sponsor, any presentation or submission for publication shall be delayed for a limited time, not to exceed 90 days, to allow for filing of a patent application or such other justified measures as the sponsor deems appropriate to establish and preserve its proprietary rights.

The investigator shall not use the name(s) of the sponsor and/or its employees in advertising or promotional material or publication without the prior written consent of the sponsor. The sponsor shall not use the name(s) of the investigator and/or the collaborators in advertising or promotional material or publication without having received his/her and/or their prior written consent(s).

The sponsor has the right at any time to publish the results of the study.

## **15 CLINICAL TRIAL PROTOCOL AMENDMENTS**

All appendices attached hereto and referred to herein are made part of this clinical trial protocol.

The investigator should not implement any deviation from, or changes of the clinical trial protocol without agreement by the sponsor and prior review and documented approval/favorable opinion from the IRB/IEC of an amendment, except where necessary to eliminate an immediate hazard(s) to clinical trial patients, or when the change(s) involves only logistical or administrative aspects of the trial. Any change agreed upon will be recorded in writing, the written amendment will be signed by the investigator and by the sponsor and the signed amendment will be filed with this clinical trial protocol.

Any amendment to the clinical trial protocol requires written approval/favorable opinion by the IRB/IEC prior to its implementation, unless there are overriding safety reasons.

In some instances, an amendment may require a change to the informed consent form. The investigator must receive an IRB/IEC approval/favorable opinion concerning the revised informed consent form prior to implementation of the change and patient signature should be re-collected if necessary.

CL:	total body clearance
C _{max} :	maximum plasma concentration
CRS:	cytokine release syndrome
CSR:	clinical study report
CV:	coefficient of variation
DBP:	diastolic blood pressure
DBS:	dried blood spots
DL _{CO} :	diffusing capacity of the lung for carbon monoxide
DP-3:	Developmental Profile 3
ECG:	electrocardiogram
ECHO:	echocardiogram
e-CRF:	electronic case report form
FEV ₁ :	forced expiratory volume in the 1 st second of the FVC maneuver
FVC:	forced vital capacity
Hb:	hemoglobin
HDL:	high density lipoprotein
HIV:	human immunodeficiency virus
HR:	heart rate
HRCT:	high resolution computed tomography
hsCRP:	high sensitivity C-reactive protein
IAR:	infusion-associated reaction

IgE:	immunoglobulin E
IgG:	immunoglobulin G
IL:	interleukin
INR:	international normalized ratio
ITT:	Intent-to treat
IV:	intravenous
LDL:	low density lipoprotein
LLOQ:	Lower Limit of Quantification
MedDRA:	Medical Dictionary for Regulatory Activities
mITT:	Modified intent-to-treat
MN:	multiples of normal
MRI:	magnetic resonance imaging
PCSA:	potentially clinically significant abnormality
PD:	pharmacodynamic(s)
PedsQL:	Pediatric Quality of Life
PFT:	pulmonary function testing
PK:	pharmacokinetic(s)
PKDM:	pharmacokinetics, dynamics and metabolism
Protime:	prothrombin time
PT:	preferred term
PTT:	partial thromboplastin time
QOL:	Quality of Life
QTc:	corrected QT-interval
QTcB:	QTc interval corrected by Bazett
QTcF:	QTc interval corrected by Fridericia
RBC:	red blood cell
rhASM:	recombinant human acid sphingomyelinase
SAE:	serious adverse event
SAP:	Statistical Analysis Plan
SAS:	Statistical Analysis System
SBP:	systolic blood pressure
SD:	standard deviation
SEM:	standard error of the mean
SI:	international system of units, international system of units
SMPD1:	acid sphingomyelinase gene, acid sphingomyelinase gene
SOC:	system organ class
$t_{1/2z}$:	terminal half-life
TEAE:	treatment-emergent adverse event
TLC:	total lung capacity
t_{max} :	time to reach Cmax, time to reach Cmax
ULN:	upper limit of normal
VAS:	visual analogue scale
VLDL:	very low density lipoprotein
V_{ss} :	volume of distribution at steady state.
WBC:	white blood cell
WHO:	World Health Organization

WHO-DRUG: World Health Organization Drug dictionary
WMW: Wilcoxon-Mann-Whitney
 β -HCG: beta-human chorionic gonadotropin

1 OVERVIEW AND INVESTIGATIONAL PLAN

This statistical analysis plan (SAP) provides a comprehensive and detailed description of strategy and statistical techniques to be used to analyze data from DFI13803, a study of GZ402665/olipudase alfa, recombinant human acid sphingomyelinase [rhASM] in pediatric patients; it is based on Amended Clinical Trial Protocol 4, dated 21-Aug-2017. The purpose of the SAP is to ensure the credibility of the study findings by pre-specifying the statistical approaches to the analysis of study data prior to database lock. This version replaces the previous versions of the SAP.

1.1 STUDY DESIGN AND RANDOMIZATION

This is a Phase 1/2, multi-center, open-label, ascending dose study to evaluate the safety, tolerability, pharmacokinetics (PK), pharmacodynamics (PD) and exploratory efficacy of olipudase alfa in pediatric patients less than 18 years of age with non-neuronopathic acid sphingomyelinase deficiency (ASMD). At least 12 patients were initially planned to be enrolled in 3 age cohorts with a minimum of 3 patients aged from 12 to <18 years (adolescent cohort), a minimum of 3 patients aged from 6 to <12 years (child cohort), and at least 2 patients aged from birth to <6 years (infant/early child cohort). At least 8 additional pediatric patients <12 years will be enrolled following protocol amendment 04 (dated 21-Aug-2017). There will be at least 20 patients enrolled in the study in total.

For each patient, study participation will consist of a screening/baseline period (up to 60 days) and a 64-week treatment period with intravenous (IV) infusions of olipudase alfa administered every 2 weeks for 64 weeks. Patients will go through a dose escalation period with target dose of 3.0mg/kg; for further details see protocol Section 1.1.

Eligible patients may enroll in a long-term study (LTS13632) following completion of the 64-week treatment period to continue receiving olipudase alfa. Patients not enrolling in the long-term study will undergo a final safety follow-up assessment by telephone 30 to 37 days after the last infusion in this study; patients with a treatment gap between the end of the 64-week treatment period of DFI13803 and enrollment in the long-term study, depending on the length of the gap, may also undergo a final safety follow-up assessment by telephone 30 to 37 days after the last infusion in this study.

1.2 OBJECTIVES

1.2.1 Primary objectives

The primary objective of this study is to evaluate the safety and tolerability of olipudase alfa administered intravenously in pediatric patients every 2 weeks for 64 weeks.

1.2.2 Secondary objectives

The secondary objectives of this study are to characterize the pharmacokinetic profile and evaluate the pharmacodynamics and exploratory efficacy of olipudase alfa administered intravenously in pediatric patients every 2 weeks for up to 64 weeks.

1.3 DETERMINATION OF SAMPLE SIZE

A sample size power calculation was not performed for this study. The study sample size is based upon empirical considerations.

1.4 STUDY PLAN

Refer to Protocol Section 1.2 for the study plan.

1.5 MODIFICATIONS FROM THE STATISTICAL SECTION OF THE PROTOCOL

In the section of statistical considerations of the protocol, the baseline for white blood cell count, platelet count, and hemoglobin was defined as the mean of 2 samples collected greater than 24 hours apart during the screening period. The baseline definition is modified in the SAP as the average of all measurements taken before the first infusion.

The statistical considerations of the protocol mentions that Infusion Associated Reactions (IAR), Acute phase reaction (APR) and cytokine release syndrome (CRS) will be listed as part of adverse events of special interest (AESI). However, per protocol, AESIs are reported as original signs and symptoms and only IARs were specifically identified in the eCRF. Consequently, APR and CRS cannot specifically be listed, but the details of these AESIs will be provided in patient narratives, and discussed in the clinical study report (CSR) as necessary.

In the section of statistical considerations of the protocol, the post-treatment period was defined as the time after the EOS visit. However, no data are expected to be collected after the EOS visit. Therefore, the post-treatment period has been removed from this SAP.

1.6 STATISTICAL MODIFICATIONS MADE IN THE STATISTICAL ANALYSIS PLAN

The main modifications made in this version of SAP compared to the previously approved version (Version 2, Dated 17-Aug-2016) are listed as follows.

- The modified intent-to-treat population was added in [Section 2.2.2](#) to be consistent with the protocol.
- The per protocol population and completer population were removed from [Section 2.2](#) as they are not pre-defined in the protocol and also are not needed for this study.

- Derivations for classifications of the different SMPD1, CHIT1 and UGT1A1 genotypes were added in [Section 2.3.1](#) in order to provide summaries on number of patients and percentages.
- Protocol-defined potential dose limiting toxicities that are considered AESIs have been added in [Section 2.6.1.3](#) to be consistent with the protocol.
- Specific analyses on infections and bleeding have been updated in [Section 2.6.1.4](#) following interactions with health authorities.
- [REDACTED]
- [REDACTED]
- The paired t-test has been updated to analysis of covariance with baseline included as covariate for exploratory efficacy variables in order to adjust for baseline, since baseline is highly correlated with change from baseline values. See [Section 2.8](#).
- Platelet count and hemoglobin were added as exploratory efficacy endpoints in order to be consistent with other ASMD studies for compound GZ402665/olipudase alfa. See [Section 2.8.4](#).

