## **8.5 METHOD OF ASSIGNING PATIENTS TO TREATMENT GROUP**

This is a single-arm treatment study whereby patients who comply with all inclusion/exclusion eligibility criteria will be enrolled. Investigator sites will access an interactive response system to confirm patient enrollment.

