#### **11.4.5 Exploratory efficacy analyses**

Efficacy assessments are described in [Section 9.2.2](#).

Efficacy analyses will be performed on the modified intent-to-treat analysis set. For each exploratory efficacy assessment, observed measures, change from baseline and/or percent change from baseline to week 52 or 64, as appropriate, will be listed and summarized using descriptive statistics overall and separately by timepoint and age cohort, including 95% confidence intervals.

Categorical variables (eg, pulmonary imaging, chest X-ray) will be summarized using frequencies and percentages according to time points collected from screening or baseline to Week 52 (or last study assessment).

The same efficacy analyses will also be performed by manufacturing scale.

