2 STATISTICAL AND ANALYTICAL PROCEDURE

Data collected in this study will be presented using summary tables, figures, and by-patient data listings. Descriptive statistics for categorical variables will be provided using frequencies (n) and percentages (%). Descriptive statistics for continuous variables will be provided using number of observations (n), mean, standard deviation (SD), median, minimum, and maximum.

If appropriate, p-values and 95% confidence intervals (CI) from analysis of covariance with baseline as covariate may be provided for change from baseline values. All data used in tabular summaries or figures will be supported by listings of underlying data – raw and/or derived, and all figures will be supported by relevant summary information.

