2.8 ANALYSIS OF EXPLORATORY EFFICACY VARIABLES

All exploratory efficacy analyses to assess changes in organomegaly (spleen and liver), infiltrative lung disease, linear patient growth, pulmonary function, bone age, cycle ergometry endpoints, physician's global assessment, efficacy biomarkers, lipid profile, bone biomarkers, health outcome questionnaires, cognitive functioning and adaptive functioning will be performed using the mITT population. For each exploratory efficacy assessment, observed measures and changes from baseline, as appropriate, will be listed and summarized, including the p-value from analysis of covariance with baseline as covariate and 95% CIs as appropriate, separately by time point, age group cohorts and overall.

Baseline for exploratory efficacy variables will be defined as the last non-missing value before the first infusion.

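### In this single-arm trial the baseline-only ANCOVA adjusts nothing, and its CIs and p-values hold only for the observed baselines; they are too optimistic for the population mean change

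*SAP*

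**What the plan says.** SAP 1.6 records the change of method: "The paired t-test has been updated to analysis of covariance with baseline included as covariate for exploratory efficacy variables in order to adjust for baseline". The reason given is "since baseline is highly correlated with change from baseline values". No correlation is stated.

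The operative sections follow:

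- SAP 2: "If appropriate, p-values and 95% confidence intervals (CI) from analysis of covariance with baseline as covariate may be provided for change from baseline values".
- SAP 2.8, for each efficacy assessment: "including the p-value from analysis of covariance with baseline as covariate and 95% CIs as appropriate, separately by time point, age group cohorts and overall".
- SAP 2.8.1 (spleen, liver) and 2.8.3 (four lung function tests) commit to baseline-covariate ANCOVA p-values for change and percent change, next to a rank test.
- SAP 2.8.2 (height Z-score), 2.8.4 (platelets, hemoglobin) and 2.8.7 (bone age minus actual age) commit to it for change.
- SAP 2.8.9 applies it to the physician's rating scored -3 to 3, with severity at screening as covariate.
- SAP 2.8.1, 2.8.3 and 2.8.4 also plan a second model, with age cohort and baseline.

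Protocol 8.5: "This is a single-arm treatment study whereby patients who comply with all inclusion/exclusion eligibility criteria will be enrolled". Protocol 11.4.5 says that efficacy results "will be listed and summarized using descriptive statistics overall and separately by timepoint and age cohort, including 95% confidence intervals"; it names no ANCOVA. SAP 1.5, which lists departures from the protocol's statistical section, does not mention the ANCOVA.

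The SAP does not say at which baseline value the adjusted mean is evaluated, which model term supplies the p-value, whether the target is the population mean or the mean at the observed baselines, or how few patients the model may be fitted to.

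**The concern.** Baseline adjustment helps when groups are compared: it removes chance imbalance and noise from the contrast. With one group there is no contrast. At the sample-mean baseline the fitted mean is the raw mean, so the estimate gains nothing, yet its standard error falls by the share of variance that baseline explains. For the population mean change, that share is real uncertainty: another sample of children would have another mean baseline and hence another mean change. The SAP's own reason for the switch, a high correlation, is the condition under which the shortening is largest.

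In the small age cohorts the dominant effect can reverse. The extra parameter uses one of very few error degrees of freedom, and the interval can become much wider.

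At stake are the CIs and p-values for spleen, liver, lung function, height, blood counts, bone age and the physician's rating. There is no control arm against which to judge them.

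**Working it through.** The documents give no power, alpha or calculated sample size, so there is no planned figure to reproduce.

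**Inputs**

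- Total: "There will be at least 20 patients enrolled in the study in total" (SAP 1.1).
- Cohort minimums: adolescents 3 (SAP 1.1: "a minimum of 3 patients aged from 12 to <18 years (adolescent cohort"); children 3 + 4 = 7; infants/early children 2 + 2 = 4 (protocol 11.1). These sum to 14 of at least 20.
- Correlation ρ of baseline with change: not given. Assumed 0.3, 0.5, 0.7, 0.9 in absolute value.
- Two-sided 95%, bivariate normal baseline and change: assumed.

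**Estimate.** Model: change = a + b × (baseline − sample mean baseline) + error. Least squares gives a = raw mean change. In one simulated data set of 20 (sample correlation −0.49), both are −7.653. The uncentred intercept, the predicted change at baseline zero, is +0.187, so the evaluation point matters.

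**Intervals**

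- Paired t: mean ± t(n−1) × s_change/√n.
- ANCOVA: mean ± t(n−2) × s_residual/√n.

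The true variance of the mean change is σ²/n, where σ² is the variance of change. The ANCOVA estimates (1−ρ²)σ²/n, so ρ²σ²/n is missing. In the simulated data set the paired CI is −9.804 to −5.501 (width 4.303) and the ANCOVA CI is −9.589 to −5.717 (width 3.872), a ratio of 0.90.

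**Coverage of the population mean change** by the ANCOVA CI = P(|t(n−2)| < t(0.975, n−2) × √(1−ρ²)). For n=20 and ρ=0.7: 2.101 × 0.714 = 1.50, and P(|t(18)| < 1.50) = 84.9%.

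**Mean width ratio** = ratio at ρ=0 × √(1−ρ²). At n=20 the ratio at ρ=0 is 1.003, so ρ=0.7 gives 1.003 × 0.714 = 0.716.

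Overall, n=20 (t multiplier 2.101 against 2.093):

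| ρ (assumed) | √(1−ρ²) | Coverage | Type I error | Width vs paired t |
|---|---|---|---|---|
| 0.3 | 0.954 | 94.0% | 6.0% | 0.96 |
| 0.5 | 0.866 | 91.4% | 8.6% | 0.87 |
| 0.7 | 0.714 | 84.9% | 15.1% | 0.72 |
| 0.9 | 0.436 | 62.8% | 37.2% | 0.44 |

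A simulation of 200,000 trials per setting agrees within 0.1 percentage point. It gives 94.9 to 95.1% for the paired t, and the same for the ANCOVA CI when the target is conditional on the observed baselines. At n=20 the ANCOVA CI is the shorter one on average once |ρ| exceeds about 0.08.

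Cohorts at their minimum size, for ρ = 0.3 / 0.5 / 0.7 / 0.9:

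| n | Error df | t, ANCOVA vs paired | Mean width ratio | Coverage |
|---|---|---|---|---|
| 3 | 1 | 12.706 vs 4.303 | 2.54 / 2.30 / 1.90 / 1.16 | 95 / 94 / 93 / 89% |
| 4 | 2 | 4.303 vs 3.182 | 1.24 / 1.13 / 0.93 / 0.57 | 95 / 93 / 91 / 80% |
| 7 | 5 | 2.571 vs 2.447 | 0.99 / 0.90 / 0.74 / 0.45 | 94 / 92 / 87 / 69% |

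The n=3 ratios are of mean widths; ratios of median widths are 2.3 at ρ=0.3 and 1.7 at ρ=0.7. With 2 evaluable patients the model has 0 error df and yields no CI or p-value. This can happen: SAP 2.11.2 analyses continuous data as observed, and SAP 2.8.3 restricts lung function testing to patients aged 5 or older, which removes most of the age range of the youngest cohort.

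**The case against.** The strongest reply is that the ANCOVA interval is not wrong as such. Given the observed baselines it has its nominal 95% coverage, and the SAP never says that its target is the population mean change. That stands, and the point is worded accordingly. But the SAP does not claim a conditional target either, the paired t-test that it replaced targets the population mean, and the protocol's plain descriptive CIs are naturally read that way.

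Second, the figures assume the mean at the sample-mean baseline. The reported p-value could instead come from an uncentred intercept, the slope or the whole model. This also stands. It adds an ambiguity to resolve and does not rescue the method.

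Third, the endpoints are exploratory, safety is the primary objective, the general wording in SAP 2 and 2.8 is conditional, and n, mean and SD are still tabulated, so the unadjusted interval can be rebuilt. All true, and this limits the weight of the point. However, SAP 2.8.1 to 2.8.4, 2.8.7 and 2.8.9 commit to the ANCOVA without that condition, and the reported intervals would still be the optimistic ones.

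Fourth, a reader might infer that the adolescent interval misleads. The calculation does not show that: at n=3 coverage is 93 to 95% for ρ of 0.3 to 0.7. The interval is needlessly wide, and the paired-t half-width is already about 2.2 SD of change, so neither tells much. Three is also a minimum, not the planned size.

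**Conclusion.** The point holds in conditional form. With one arm and evaluation at the model's mean baseline, the ANCOVA returns the raw mean change with a standard error that treats the baselines as fixed. For the population mean change at n=20, the nominal 95% CI covers about 94, 91, 85 and 63%, and a nominal 5% test has type I error of about 6, 9, 15 and 37%, for correlations of 0.3, 0.5, 0.7 and 0.9. In a cohort of 3 the interval is instead 2.5 to 1.9 times as wide on average for correlations of 0.3 to 0.7.

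The result rests on the assumed correlations and on bivariate normality. The entry criteria truncate two baselines (spleen volume at least 5 multiples of normal, height Z-score −1 or lower), so exact coverage will differ. The SAP asserts high correlation for change only; nothing is said about percent change.

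Two stronger readings are not supported. One is that more than a third of the efficacy tests would be false positives: 37% is the far end of an assumed range, and the plan makes no confirmatory efficacy claim. The other is that Version 2 of the SAP is known to have been right: only one line of the change list describes it.

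**What to change.** - In SAP 2, 2.8, 2.8.1, 2.8.2, 2.8.3, 2.8.4 and 2.8.7, take the 95% CI and p-value for the mean change from the one-sample (paired) t-test, overall and by cohort. Do the same for percent change only where ANCOVA is already planned on it: spleen, liver and lung function.
- In SAP 2.8.9, give the one-sample t CI for the mean rating on the -3 to 3 scale. That rating has no paired difference and no percent change.
- Keep ANCOVA for the age-cohort models in SAP 2.8.1, 2.8.3 and 2.8.4, where groups are compared.
- If a baseline-only ANCOVA stays as supportive, state its evaluation point and target, and add slope² × variance of baseline/n to the variance. That restores 95.2 to 95.6% coverage at n=20. It over-covers in tiny cohorts (about 99.6% at n=3), so also set a minimum number of patients for the model.

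Cost: SAP wording only, with no change to data collection. The overall CIs become wider. At n=20 the mean half-width rises to 0.462 SD of change from 0.442, 0.401, 0.331 or 0.202 at correlations of 0.3, 0.5, 0.7 or 0.9, that is by a factor of 1.05, 1.15, 1.40 or 2.29.
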